## **Group B Investigational Efficacy Objectives:**

- 1. Evaluate the efficacy of treatment with COVID-19 convalescent plasma in relation to the amount of Anti-SARS-CoV-2-spike protein IgA as assayed by the EUROIMMUN Anti-SARS-CoV-2 assay.
- 2. Evaluate the efficacy of treatment with COVID-19 convalescent plasma in relation to the amount of both Anti-SARS-CoV-2-spike protein IgG and IgA as assayed by the EUROIMMUN Anti-SARS-CoV-2 assay.

All primary and secondary efficacy endpoints for Group B will be re-evaluated based on levels of IgA for investigational objective #1 and based on combined levels of IgG and IgA for investigational objective #2

**Primary Safety Objective for Group A and B:** Evaluate the safety of treatment with COVID-19 convalescent plasma in relation to the amount of Anti-SARS-CoV-2-spike protein IgG as assayed by the EUROIMMUN Anti-SARS-CoV-2 assay.

# **Primary Safety Endpoints:**

- Rapid deterioration of respiratory or clinical status on transfusion of COVID-19 convalescent plasma
- 2. Development of increased cytokine storm activity within 48 hours of receiving a unit of COVID convalescent plasma.

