#### 2.2 Data collection

The following data points will be gathered for all patients in the study while inpatient. Patients discharged prior to 28 days will receive a phone call to determine their 28 day outcome and patients enrolled in the study will be monitored for 90 days from discharge to determine if there is a readmission and the reason for the readmission.

**COVID-19 Presentation:** Collected on enrollment, see form on page 30.

**Demographics**: Collected on enrollment, see form on page 31.

Medical History: Collected on enrollment, see form on page 31.

Concomitant Medications: Collected on enrollment, see form on page 31.

Vital Signs: Collected daily from enrollment to discharge, see form on pages 30 and 32. Laboratory Values: Collected daily from enrollment to discharge, patient is required to have a CBC with differential, a CMP, a ferritin and a CRP. On enrollment and weekly the patient must have an IL-6, D-Dimer, procalcitonin, LDH, fibrinogen, ESR, and CK. IL-6 and LDH, other laboratory values will be recorded when obtained through standard of care. See form on page 32.

Clinical Status: Collected daily from enrollment to discharge, see form on page 32.

**Medications:** Collected daily from enrollment to discharge, see form on page 33.

Serology Values: Collected per schedule, see form on pages 34 and 35.

PCR Values: Collected per schedule, see form on page 36

Safety Data: Collected for first 24 hours after transfusion, see form on page 37.

**Outcomes:** Collected at discharge or death, see form on pages 38 and 39.

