#### **Sources of Materials**

Participants will provide the required blood samples at the indicated time points, as described in the Research Strategy, and outlined in the above schedule of events (**Section 2.4**). Additional participant data will be obtained through a chart review within Beaumont's EMR (EPIC) and supplemented where appropriate by patient completion of interviews.

All patients enrolled in the study will be followed daily while inpatient by research coordinators who will gather all required data.

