#### **Adverse Events:**

An adverse event (AE) can be any unfavorable and unintended sign (including an abnormal laboratory finding), symptom, or disease temporally associated with the use of an investigational product, whether or not considered related to the investigational product.

The occurrence of an AE may come to the attention of study personnel during at any point in the study. The period of observation for which AEs are to be collected will begin after the subject has signed the ICF and will continue throughout their participation in the study. All AEs, whether reported by the subject or noted by study personnel, will be recorded in the subject's research chart.

Information to be collected includes event description, time of onset, investigator's assessment of severity, investigator's assessment of relationship to study drug, and time of resolution/stabilization of the event. All AEs occurring while on study will be documented appropriately regardless of their relationship to the study treatment. AEs will be followed to adequate resolution.

Any medical condition that is present at the time that the subject is screened will be considered as baseline and not reported as an AE. However, if the condition deteriorates at any time during the study, it will be recorded as an AE. Any laboratory abnormality not considered to be clinically significant by the investigator will not be considered an AE. All AEs will be graded for intensity and relationship to the study treatment.

One of the investigators will determine the relationship between the study treatment and the occurrence of an AE as defined below:

- Definitely related events are those that the investigator determines are definitely related to the intervention, and for which the investigator believes no alternative etiology exists.
- Probably related events are those for which the investigator believes there is a reasonable likelihood the AE may have been caused by the intervention involved in the research.
- Probably not related events are those for which the investigator believes there
  is a reasonable likelihood the AE may have been caused by other factors and
  not caused by the intervention involved in the research.

- Unrelated events are those that the investigator determines are not related to the intervention either due to timing or a confirmed alternative cause.

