# ABACCuS SARS-CoV-2 RT PCR Data Collection Form:

Patient Initials/Study ID: _		Date of Enrollment:
Plasma Unit Used:		Date and Time of Transfusion:
Patient Qualifying RT PC	R:	
Result:	CT Value:	Date and Time of Specimen:
Patient Pre-Transfusion F	RT PCR:	
Result:	CT Value:	Date and Time of Specimen:
Patient 24 hour Post-Tran	nsfusion RT PCR:	
Result:	CT Value:	Date and Time of Specimen:
Patient 72 hour Post-Tran	nsfusion RT PCR:	
Result:	CT Value:	Date and Time of Specimen:
Patient 7 Days Post-Tran	sfusion RT PCR:	
Result:	CT Value:	Date and Time of Specimen:
Patient 14 Days Post-Tra	nsfusion RT PCR:	
Result:	CT Value:	Date and Time of Specimen:
Signature of coordinator		 Date
engination of occidentation		Dato
Signature of Investigator	reviewing data	Date

ABACCuS 28 Safety Form:					
Patient Initials/Study ID:	Date of Enrollment:				
Plasma Unit Used:	Date and Time of Transfusion:				
In the 2 hours after the transfusion: Did the patient have a rapid decline in respiratory status: Y	/N				
If yes: Date and Time:	Severity:				
If yes: Description of the event:					
Did the patient have a rapid decline in clinical status: Y/N					
If yes: Date and Time:	Severity:				
If yes: Description of the event:					
In the 4 hours after the transfusion: Did the patient have a fever of >38 $^{\circ}$ C: Y/N $T_{max}$ : _	If yes: Date and Time:				
Did the patient have an allergic reaction: Y/N  Conjunctival Edema: Y/N Edema of Oral Area: Y/N  Generalized Flushing: Y/N Hypotension: Y/N  Maculopapular Rash: Y/N Pruritus (itching): Y/N  Urticaria (hives): Y/N	Localized Angioedema: Y/N				
In the 6 hours after the transfusion: Was the patient diagnosed with Transfusion Associated Cir	rculatory Overload (TACO): Y/N				
If yes: Date and Time:	Severity:				
Was the patient diagnosed with Transfusion Related Acute	Lung Injury (TRALI): Y/N				
If yes: Date and Time:	Severity:				
In the 24 hours after the transfusion: Did the patient have evidence of cytokine storm: Y/N					
If yes: Date and Time:	Severity:				
If yes: Description of the event:					
Signature of coordinator	Date				
Signature of Investigator reviewing data	Date				

ABACCuS 28 Day Ou	tcome Form Gro	oup A:						
Patient Initials/Study ID:			Date of Enrollment:					
Plasma Unit Used:			Date a	Date and Time of Transfusion:				
Primary Outcome:								
Was the patient intuba	ted within 28 days	s of the transfus	ion: Y/N					
If intubated: Date of intubation:				Day #:				
Secondary Outcomes	5 :							

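### Primary safety endpoint 2 runs to 48 hours after transfusion, but the safety-data rule and the safety form's cytokine-storm item stop at 24 hours

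*Combined protocol and SAP*

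**What the plan says.** Section 2.1 lists two primary safety endpoints. The second is "Development of increased cytokine storm activity within 48 hours of receiving a unit of COVID convalescent plasma". The primary safety objective, for both groups, relates safety to the amount of anti-spike IgG in the transfused unit. The investigational safety objectives repeat this for IgA and for IgG and IgA combined.

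Section 2.2 gives the collection rule for safety data: "Collected for first 24 hours after transfusion, see form on page 37". The safety form asks: "In the 24 hours after the transfusion: Did the patient have evidence of cytokine storm: Y/N". A *Yes* opens fields for date and time, severity and description.

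Other provisions also bear on hours 24 to 48. For daily laboratory work, Section 2.2 says the "patient is required to have a CBC with differential, a CMP, a ferritin and a CRP", and clinical status is recorded daily up to discharge. The schedule in Section 2.4 marks adverse event monitoring as daily. Under Sources of Materials, enrolled patients "will be followed daily while inpatient by research coordinators who will gather all required data". The Adverse Events text says "Information to be collected includes event description, time of onset", and of a condition already present at screening, "if the condition deteriorates at any time during the study, it will be recorded as an AE". It also says: "Any laboratory abnormality not considered to be clinically significant by the investigator will not be considered an AE".

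**The concern.** The endpoint and the instrument designated to collect it have different time limits. If staff follow Section 2.2 and answer the form as worded, a first onset after hour 24 is a non-event on the form, even though it falls inside the endpoint's window. If the analyst builds the endpoint from adverse event records or daily laboratory values, the same patient may be an event. Two analysts could each follow the protocol and produce different event lists.

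This matters because it is one of only two primary safety endpoints, and it is to be related to unit IgG and then again to IgA and to both together. The risk discussion in Section 4.1 raises harm at both low and high antibody levels as the reason for studying a range. An endpoint with that purpose needs one window and one stated source.

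**Working it through.** The plan has no figure of its own to reproduce. The check is a comparison of windows, one subtraction, and a review of what else covers the gap.

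**Inputs**

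- Endpoint window: 48 h (Section 2.1, Primary Safety Endpoints, item 2).
- Safety-data period: 24 h (Section 2.2, Safety Data).
- Form item window: 24 h (safety form, cytokine-storm item). It is the only item on that form about cytokine storm. The shorter windows serve other events (rapid decline, fever and allergic reaction, TACO and TRALI) and are not counted here.

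**Gap**

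- Uncovered time = 48 h − 24 h = 24 h.
- Share of the endpoint window = 24 / 48 = 50%.

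**Test case: first onset at hour 30**

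- Endpoint: 30 ≤ 48, so the onset is in time.
- Form item: 30 > 24, so the answer is *No*.
- The same disagreement arises for any first onset after hour 24 and up to hour 48.

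**What else runs through hours 24 to 48, and its limits**

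| Record | Covers the gap? | Limit for this endpoint |
|---|---|---|
| Daily CBC, CMP, ferritin, CRP (2.2, 2.4) | Yes, while an inpatient | No rule turns the values into an event |
| Daily clinical status and daily form | Yes, while an inpatient | The form has no cytokine-storm item |
| IL-6 | No required draw | Required only at enrollment and weekly |
| Adverse event records, with time of onset | Yes | Laboratory changes judged not clinically significant are left out |
| Group A outcome forms, cytokine-storm item | Yes | Date only, no clock time; asks for evidence, not an increase |

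A date without a clock time cannot always settle the endpoint, because hour 48 normally falls partway through a calendar day.

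**Link to the endpoint**

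The protocol does not name any of these records as the source for primary safety endpoint 2. Section 3.1 mentions cytokine storm once, among the binary secondary outcomes, with no window or source.

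**Wording**

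The endpoint requires an *increase*; the form item asks only for *evidence*. The endpoint names no comparator, and no definition of increased cytokine storm activity appears anywhere. Extending the time limit alone would therefore not make the item match the endpoint.

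**The case against.** The strongest reply is that the chart does not close at hour 24. Ferritin, CRP, CBC and CMP continue daily, clinical status is recorded daily, and coordinators follow every inpatient. Adverse events are monitored daily with time of onset, and a baseline condition that worsens is itself recorded as an adverse event. The attending team is expected to report significant worsening (Data and Safety Monitoring Plan), and the general data source is the electronic medical record. A cytokine storm at hour 30 would probably leave a trace.

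Most of this stands. A reader might infer from the mismatch that nothing is collected after hour 24, or that such events are lost. The documents do not support either reading. They do support a narrower statement: the records exist, but the plan does not say which of them decides this endpoint or by what criterion, and the one form it designates for safety data gives the wrong answer for those hours.

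It may also be said that the slip could lie in the 48-hour endpoint and not in the 24-hour collection text. That is fair; the documents do not show which was intended. It changes the direction of the correction but not the need for one.

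**Conclusion.** The inconsistency is real and should be corrected. The endpoint runs to 48 hours, while the collection rule and the form item run to 24, and no text reconciles them. The mismatch covers 24 of 48 hours. The finding assumes that the form is answered as worded, and it concerns first onsets after hour 24.

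The 50% should not be read as half of the events or half of the data. The documents do not say how many onsets to expect in hours 24 to 48, so no loss is quantified and none is claimed. Nor does the endpoint say that the increase is measured from pre-transfusion status. That is one plausible reading, and the sponsor has to state the comparator. No Group B outcome form appears in the text available for review, so nothing is concluded about it.

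**What to change.** 1. Bring Section 2.1 (primary safety endpoint 2), Section 2.2 (Safety Data) and the safety form's cytokine-storm item to one window. The simplest way is to extend the Section 2.2 period for cytokine storm and the form item's heading to 48 hours, to match the stated endpoint.
2. Reword the item to ask about an increase. State the comparator and the criterion, preferably using markers already drawn daily.
3. Name the record that decides the endpoint analysed against unit IgG. Do this before unblinding to antibody level; Section 2.5 keeps that blind until study closure and formal data analysis. Which record decides is the sponsor's choice.

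The cost is one sentence in Section 2.2, one form heading with its item wording, and one sentence on source and criterion. The item already has fields for date and time, severity and description, so no new fields are needed. No new draws are needed if the criterion uses the daily markers. A criterion based on IL-6 could need one, because no IL-6 draw is required between enrollment and the first weekly sample.

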#### 2.4 Schedule of events

Study Period	Screening	Baseline	Treatment		Follow Up a					
Day	-1 to 0	0	0	D	1	3	7	14	21	28
Eligibility								,	,	
Inclusion/Exclusion	Х									
Informed consent	Х									
Demographics and	V									
medical history form	X									
Initial data collection	Х									
form	^									
Type and Screen	Х									
Pregnancy Test	Х									
Study Procedures										
Plasma transfusion			X							
Vital signs			Xp							
Physical exam c	X		Xd		Χ		Χ			
Daily vital signs, clinical										
and laboratory values				Χ						
form										
Daily medications form				Χ						
Adverse event		X	X	Х						
monitoring				^						
Serology collection form		X	X		Χ	Χ	Χ	Χ	Χ	Xe
Outcome form										Xf
Laboratory Testsg				_	•	,	,			•
CBC with differential		X		Χ						
CMP		Χ		Χ						
Ferritin		Χ		Χ						
Fibrinogen		Χ					Χ	Χ	Χ	Χ
CRP		Χ		Χ			Χ	Χ	Χ	Χ
ESR		Χ					Χ	Χ	Χ	Χ
Creatine Kinase		Χ					Χ	Χ	Χ	Χ
D-Dimer		Χ					Χ	Χ	Χ	Χ
LDH		Х					Χ	Χ	Χ	Χ
Interleukin-6		X					Χ	Χ	Χ	Χ
Triglycerides		Χ					Χ	Χ	Χ	Χ
Procalcitonin		Χ					Χ	Χ	Χ	Χ
Anti-SARS-CoV-2 IgA			X h		Χ	Χ	Χ	Χ	Χ	Xi
Anti-SARS-CoV-2 IgG			X h		Χ	Χ	Χ	Χ	Χ	Xi
SARS-CoV-2 RT PCR			Xj		Χ	Χ	Χ	Χ		

- a Column D are obtained daily, day 1 and 3 are obtained 24 hours (+/- 1 hour) from transfusion end, day 7, 14, 21, and 28 are obtained any time on that calendar day.
- b Standard vital signs for transfusion of blood products will be performed.
- c Given the issues with isolation and PPE, the exam of the attending physician's team or the pulmonary critical care team can be used.
- d Only if needed due to acute reaction.
- e After 28 days will be collected every 7 days +/- 1 day till discharge.
- f Outcome form to be filled out on final day of admission if prior to 28 days or at 28 days, after 28 days a second outcome form to be filled out on final day of admission, readmission will be tracked for 90 days.
- g All laboratory tests from this list which are obtained as standard of care will be tracked, baseline labs within 24 hours are acceptable and do not need to be reordered.
- h To be drawn within 1 hour prior to transfusion and 1 hour post-transfusion completion (no earlier than 1 hour but up to 75 min post transfusion).
- i After day 28 this will be drawn every 7 days +/- 1 day while participant remains hospitalized.
- j To be obtained within 1 hour prior to transfusion.

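### Primary safety endpoint 2 is an increase in cytokine storm activity within 48 hours, but the safety form scores presence only, for 24 hours, and no analysis against IgG is specified

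*Combined protocol and SAP*

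**What the plan says.** Section 2.1 sets a primary safety objective for both groups: "Evaluate the safety of treatment with COVID-19 convalescent plasma in relation to the amount of Anti-SARS-CoV-2-spike protein IgG", measured by the EUROIMMUN assay. Two primary safety endpoints follow. The first is rapid respiratory or clinical deterioration on transfusion. The second is "Development of increased cytokine storm activity within 48 hours of receiving a unit of COVID convalescent plasma". No marker, threshold or comparator is given for the increase.

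The data for the second endpoint come from these places:

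- **Safety form.** Under "In the 24 hours after the transfusion" it asks "Did the patient have evidence of cytokine storm: Y/N". If the answer is yes, it also takes date and time, severity and a description.
- **Section 2.2, safety data.** "Collected for first 24 hours after transfusion".
- **Section 2.2, daily laboratory values.** From enrollment to discharge the "patient is required to have a CBC with differential, a CMP, a ferritin and a CRP".
- **Section 2.2, other markers.** "On enrollment and weekly the patient must have an IL-6, D-Dimer, procalcitonin, LDH, fibrinogen, ESR, and CK".
- **Section 2.4, schedule of events.** CBC, CMP, ferritin and CRP are marked at baseline and in the daily column ("Column D are obtained daily"). IL-6, D-dimer, LDH and fibrinogen are marked at baseline and then on days 7, 14, 21 and 28. Standard-of-care results for the listed tests are tracked.

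Section 3.1 specifies models for the two primary efficacy outcomes, the secondary outcomes and the investigational outcomes. It lists evidence of cytokine storm among the binary secondary outcomes. It specifies no analysis of either primary safety endpoint.

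**The concern.** The endpoint is a change over 48 hours, and the form item is a state over 24 hours. Enrolled patients need more than 6 L of oxygen or are intubated, and Section 1.1 describes severe disease as an overwhelming inflammatory response, so some may well be in a storm when the unit is given. A yes for such a patient says nothing about what the unit did. Because the IgG content is unknown when the unit is assigned, prevalent storms should fall about equally across IgG levels. They would then add events unrelated to IgG and weaken any real gradient.

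This matters because the protocol raises the question itself. Its section on hypothetical risks warns of harm from antibody levels that are too low and too high, and presents the study as able to detect level-related worsening. If the endpoint is not defined and its analysis not chosen in advance, the definition will be settled after the antibody levels are known, or the endpoint will only be tabulated.

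**Working it through.** **1. Windows side by side.** The endpoint runs 48 hours. The form item and the Section 2.2 safety collection period both run 24 hours. The form covers 24/48 = 50% of the endpoint window.

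**2. Required draws inside 48 hours.**

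| Marker | Baseline | Required draws, 0–48 h | Next required draw |
|---|---|---|---|
| IL-6, D-dimer, LDH, fibrinogen | yes | 0 | day 7 (168 h, which is 120 h after the window closes) |
| CRP, ferritin | yes | about 2 each while in hospital | daily |

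Procalcitonin, ESR and CK follow the first row. CBC and CMP follow the second, but of the daily tests CRP and ferritin are the inflammatory markers.

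**3. What prevalent storms do to the Y/N item.** The plan has no figure to reproduce here. The following are assumptions: the 500 planned patients split at median IgG, so n = 250 per half; complete data; a two-sided 5% test (the documents set no level for safety endpoints); new-storm rates of 10% and 19% among patients free of storm at transfusion; and a prevalent fraction π, equal in both halves, all scored yes.

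Recorded rate: p = π + (1 − π) × new-storm rate.

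- π = 0: 10% and 19%.
- π = 20%: 0.20 + 0.80 × 0.10 = 28.0%, and 0.20 + 0.80 × 0.19 = 35.2%.
- π = 40%: 0.40 + 0.60 × 0.10 = 46.0%, and 0.40 + 0.60 × 0.19 = 51.4%.

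Power = Φ{(|p2 − p1| − 1.96·SE0)/SE1}, where SE0 = √[2p̄(1 − p̄)/n] and SE1 = √[p1(1 − p1)/n + p2(1 − p2)/n].

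| π | Difference | SE0 | SE1 | Power |
|---|---|---|---|---|
| 0 | 0.090 | 0.0315 | 0.0312 | 81.7% |
| 20% | 0.072 | 0.0416 | 0.0415 | 40.9% |
| 40% | 0.054 | 0.0447 | 0.0446 | 22.6% |

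For the first row: (0.090 − 1.96 × 0.0315)/0.0312 ≈ 0.90, and Φ ≈ 0.82. Power falls because the difference shrinks and the variance rises.

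**4. What the daily markers could detect.** For a continuous baseline-adjusted change in 500 patients, the correlation detectable with 80% power is about (1.96 + 0.84)/√500 = 0.125. Between two halves that is 2 × 0.125 = 0.25 residual SD. On a latent normal scale the Y/N item, even with no prevalent storms, detects about 0.40 SD at a 10% base rate and about 0.32 SD at base rates of 30% to 50%. The scales are not the same, so the comparison is only indicative.

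**The case against.** The best reply is that the record as a whole holds more than the tick box. CRP and ferritin are drawn at baseline and daily and have fields on the daily form. That form also has fields for IL-6, D-dimer, LDH and fibrinogen when standard care supplies them. A yes on the safety form brings severity and a description. Worsening of a condition present at screening is to be recorded as an adverse event. Section 3.1 also gives a spline logistic model on IgG for evidence of cytokine storm as a secondary outcome.

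Most of this stands, and it rules out two stronger readings. A reader might infer that an increase in storm activity is neither recorded nor measurable. The documents do not support that, because it is measurable on CRP and ferritin. A reader might also infer that the whole primary safety objective rests on one Y/N item. It does not: the first safety endpoint has its own form items, and the serious adverse events listed as a secondary objective are collected as well.

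The reply leaves three gaps. Nothing says how those records are turned into a value for endpoint 2. The 24- and 48-hour windows conflict. The secondary-outcome model concerns presence of a storm as an efficacy outcome, not an increase within 48 hours. A fair further objection is that CRP and ferritin do not fully represent cytokine storm and should not replace clinical judgement. For that reason the marker analysis belongs beside the item, not in its place.

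**Conclusion.** The concern holds as a gap in definition, window and analysis, not as an absence of data. Followed literally, the safety form can count storms already present at transfusion and omits the second half of the endpoint window. Section 3.1 relates neither primary safety endpoint to IgG.

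The mismatches in wording, window and analysis are read directly from the documents. The loss of power is illustrative: from 82% to about 41% and 23% at 20% and 40% prevalence. It depends on assumed event rates, on every prevalent storm being scored yes, and on equal prevalence across IgG halves. If site staff already read the item as new or worsened activity, the loss would be smaller, but the form does not tell them to. This should be corrected before unblinding. The data already required make that possible.

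**What to change.** 1. Reword the safety form item to ask whether cytokine storm activity is *new or increased since transfusion*.
2. Reconcile the 24-hour window in Section 2.2 and on the safety form with the 48 hours in the endpoint.
3. Add to Section 3.1, fixed before unblinding, an analysis of change in log CRP and in log ferritin from the last pre-transfusion value to the highest value on days 1–2. Regress each on unit IgG with a spline, so that harm at either end of the range can show, with the baseline value and group (A or B) as covariates. Report it alongside the reworded item.
4. State in Section 3.1 how the reworded item and the first primary safety endpoint will each be related to IgG.

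The cost is protocol and SAP text and a small form revision covering the wording and the window. No new draws are needed. The drawback is that two markers represent cytokine storm only in part, which is why the clinical item stays.
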